4.2 SCIENTIFIC RATIONALE FOR STUDY DESIGN

The NIRVANA Protocol describes a trial design to provide pilot data on the potential efficacy of nicotinamide riboside (NR) for the treatment of incident AKI or AKI severity in patients with COVID-19 infection admitted to the hospital while receiving available or usual standard of care.

AKI in patients with SARS-CoV-2 is being increasingly recognized as a major risk factor of morbidity and mortality. The incidence of patients with AKI ranged between 22% to 46% in independent analyses of inpatients with SARS-CoV-2 in NYC [24]. Recently, data from the Northwell Health System, NYC reported that 90% of COVID-19 patients on mechanical ventilation developed AKI [23]. The Mount Sinai Health System [24], also from NYC, documented a 3 times higher incidence of Stage 3 AKI vs Stages 1 or 2. In addition to these

extremely high morbidity indices for AKI, data from a single center in Wuhan, China reported a mortality hazard ratio of 4.7 in Stage 3 AKI patients [59]. Similar findings were found by Mount Sinai with a 52% mortality rate in patients with AKI, compared to mortality of only 9% in those without AKI admitted to the ICU. Surprisingly, 44% of SARS- COVID-19 patients with AKI did not fully recover kidney function by the time of discharge from the hospital [24]. Recent data suggest that mortality is lower in hospitalized patients with COVID-19 [25]. Therefore, strategies to identify and treat patients with impending AKI will be of major value to reduce mortality, hospital length of stay, hospital costs and potential progression to CKD.

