5.5 STRATEGIES FOR RECRUITMENT AND RETENTION

Participants will be recruited from three participating sites: the University of Texas Health San Antonio (UTHSA), Icahn School of Medicine at Mount Sinai, New York, NY, and University of Washington (UW), Seattle, WA. The single IRB (sIRB) at the Washington University in St. Louis (FWA00002284) will serve as the Central IRB for all three participating sites. We will recruit and consent eligible participants and will advance them into the Treatment Period. A total of 100 participants will be randomized.

Each participating site and the coordinating site (UTHSA) will contribute to recruitment of study participants. Recruitment methods will focus primarily on the selection of eligible participants via identifying patients admitted to the respective hospitals with a diagnosis of COVID-19. Lead investigators at each site are physician scientists who will have direct access to eligible participants. For efficient recruitment, each site will employ the following approaches. After a COVID-19 patient is admitted to the hospital with a new positive laboratory diagnosis of COVID-19, the study team members will be notified by the COVID-19 Admitting Team. All

three participating sites also maintain a COVID-19 database which is updated every 6-8 hours and a designated study member will review the COVID-19 database twice a day. Each study team will have access to the respective hospital COVID-19 admission logs and EHR enabling them to review several eligibility criteria. The study investigators or clinical coordinators will approach the potentially eligible participants or LAR (when appropriate) and inform them of the study protocol. All participants will provide written consent for participation in the study. Sites have the ability to use one of the FDA approved options for obtaining written signature during a pandemic, based on their institutional requirements.

During consenting process, each participant will receive clear and detailed information about the NIRVANA study with an emphasis on risks, benefits, and alternative to enrollment. Participants will be given opportunities and time to learn about ongoing clinical trials for COVID-19 and their eligibility to enroll in another competing study. Voluntary participation will be discussed and participants will be allowed to withdraw from the current study at any time point after providing consent.

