6 STUDY INTERVENTION

6.1 STUDY INTERVENTION(S) ADMINISTRATION

6.1.1 STUDY INTERVENTION DESCRIPTION

Baseline Visit (Day 1)

After obtaining consent, baseline visit procedures will be performed as listed in Table 1 (Schedules of Activities in Section 1.3). Participants will be randomized after abstracting the following data from the EHR: sociodemographic, contact information, medical/surgical history,

comorbidities, and routine medications on admission, standard of care at hospital, home medications, all concomitant medicines including dietary or nutritional supplements and over-the-counter medications, vitals and physical examinations, routine laboratory test results.

Randomization will be accomplished through the use of an online randomization service. Participants will be randomly allocated to 1:1 ratio to receive either nicotinamide riboside (NR) or placebo. Only the study statisticians (Drs [name] and [name]) and the local hospital Research Pharmacists will have access to the randomized assignment for the purpose of tracking randomization and study drug dispensing, respectively. Study investigators and study participants will be blinded to the intervention assignments. Neither the statisticians nor the pharmacist will have direct contact with the study participants.

Eligible study participants enter intervention phase after consenting to the study protocol:

- Nicotinamide riboside (NR, Niagen[®]) or placebo will be administered orally (or via nasogastric tube) 500 mg twice a day for 10 days during hospitalization or prescribed for at home administration if discharged before 10 days from the hospital.
- Placebo capsule manufactured by ChromaDex to match NR or Niagen®

TREATMENT PERIOD

All measures related to study treatment visits are harmonized to standard of care to minimize care interruption and disruption to hospital staff workflow. Most of the treatment procedures are standard of care or routine procedures for COVID-19 participants in an acute care setting. These data will be obtained from the EHR. If any treatment procedure is not available through the EHR, the study team will obtain these data from the primary care team or directly from the participant. Where multiple results are present in the EHR, they will all be recorded in the study database so that all relevant values are captured. A summary of the trial's schedule of event is included in Table 1 (Section 1.3).

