- Demographics (age, sex, race, and ethnicity)
- Vitals and respiratory parameters
- Physical examination
- Comorbidities
- Acute signs and symptoms
- Parameters to assess severity-of-disease using the Acute Physiologic and Chronic Health Evaluation (APACHE) II classification, as applicable
- Current use of home and inhospital medications including over-the-counter
- Receipt of open label study medication
- Receipt of invasive procedures
- Blood and urine collections and analyses (see Table 4)
- Other procedures as per the Schedule of Events (see Section 1.3 Table 1)

Study intervention period (daily):

- Date and time of randomization
- Drug administration and accountability
- Vitals and respiratory parameters
- Physical examination
- Comorbidities
- Acute signs and symptoms
- Review of current medications
- Receipt of invasive procedures
- Hospital data including adverse events, endpoints, and outcomes

Nicotinamide Riboside for AKI in COVID-19 positive inpatients Protocol #: Not yet assigned

- Collect hospital data to complete APACHE-II
- Blood and urine collections and analyses (see Table 4)
- Other procedures as per the Schedule of Events (see Section 1.3 Table 1)

Assessments following Hospital Discharge: Early discharge (before completing 10-day intervention) and Follow-up visits

Early discharge: Using daily phone call or videoconferencing, following data will be collected

- Drug accountability
- Vitals and respiratory parameters
- Comorbidities
- Acute symptoms
- Review current medications
- Query about adverse events, endpoints, and outcomes
- Review EHR for additional data, if applicable
- Fingerstick blood creatinine using the POC device will be performed by the participant/care provider until Day 10 (see Table 4)
- Daily urine collections for biorepository (see Table 4)
- Blood collection will be done on Day 10 for research laboratory analysis and biorepository (see Table 4)
- Other procedures as per the Schedule of Events (see Section 1.3 Table 1)

Assessments for participants with early hospital discharge

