Missing data can threaten the inferences made about study questions. The study team will make every effort to minimize the impact of missing data, including attempting to obtain final information on participants even if adherence to study procedures is poor or they do not follow the randomized treatment. In cases where missing data is unavoidable, we will use multiple imputation using chained equations to impute outcomes and relevant covariates to mitigate the potential impact of missing data, combining across imputations with Rubin's rules to account for the variability in the imputation procedure [84]. Any data point that appears erroneous or inexplicable based on clinical judgement will be investigated by study staff. If data points are considered to be outliers then sensitivity analyses will be carried out with and without the suspected outlier. Under the missing at random (MAR) assumption the estimates provided by our planned repeated measures statistical models using maximum likelihood estimation will be asymptotically unbiased [85].

All data will be summarized by treatment and clinical site in all randomized participants. Statistical estimates of treatment effects (with 95% confidence intervals, where appropriate), and p-values will be tabulated. All statistical tests will be two-sided with a significance level of 5%. R and/or SAS will be used throughout. Due to the overall exploratory nature of this study corrections for multiple comparisons will not be applied.

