The primary analysis will be based on a cumulative logit model for ordinal data of the primary outcome with terms for treatment, age, gender, clinical site, and baseline serum creatinine. The proportional odds assumption will be tested with a score statistic and empirical logit plots. If the proportional odds assumption is violated then the analysis will be conducted under a partial proportional odds assumption. Under a partial proportional odds assumption, three odds ratios will be estimated; if evidence suggests that the proportional odds assumption holds, a single odds ratio will summarize the treatment effect. In either case, the odds ratio estimate(s), 95% confidence interval(s), and p-value(s) will be reported. Further study will be indicated if the p-value for any treatment effect suggesting benefit in the NR arm is less than or equal to 0.05.

SECONDARY END POINT: Major Adverse Kidney Events (MAKE)

The null hypothesis is H₀:HR=1 where HR is the ratio of the hazard of MAKE with NR treatment to the hazard of MAKE with Placebo treatment. We expect that HR will be less than 1. MAKE is defined as Yes if a doubling of serum creatinine (from baseline), the initiation of long-term dialysis, or death from any cause is observed, and No otherwise. Treatment arms will be compared with regard to the time to the first occurrence of MAKE over the entire duration of the study from baseline to 90 days post-randomization with proportional hazard models of time to MAKE in terms of treatment without and with adjustment for age, race, clinical site, baseline

serum creatine. The coefficients, standard errors and 95% confidence intervals and corresponding hazard ratios will be reported without and with adjustment for covariates. The proportional hazards assumption will be assessed with Schoenfeld residuals and log survival plots. The unadjusted model will be graphically summarized with overlaid Kaplan Meier curves and the p-value for the corresponding log rank test. Covariate interactions with treatment will be of interest and will be explored.

SECONDARY END POINT: Kidney impairment as indicated by eGFR and proteinuria at 30 and 90 days

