The null hypothesis to be tested is H_o : $R_{NR}=R_{Placebo}$, where R_{NR} and $R_{Placebo}$ are the mean rates of change of eGFR in patients randomized to NR or to Placebo respectively from baseline to day 30 and day 90. We expect the eGFR rate of change to be increased with NR relative to Placebo. The same hypothesis will be tested for proteinuria, using log-transformed urinary albumin-to-creatinine ratio, where we expect the mean proteinuria rate of change to be decreased with NR relative to Placebo.

We will quantify kidney dysfunction at 30 days and 90 days post-randomization, measured by eGFR calculated by the CKD-EPI (the Chronic Kidney Disease Epidemiology Collaboration) equation [87] and the urine protein/creatinine ratio (PCR). To address non-ignorable missingness due to dialysis, death, or withdrawal of consent, all of which may be considered as informative censoring, the statistical method will be the same as that specified for NAD+.

eGFR will be evaluated untransformed, while urine PCR will be log-transformed to evaluate percent change because urine PCR is highly skewed and relative changes in urine PCR are proportional to risk of adverse renal and cardiovascular outcomes. We will include time, treatment, and interactions of treatment with time as independent variables in a mixed effects linear model. We will focus on the coefficient for the interaction of treatment with time as the primary measure of treatment effect. We will consider a p-value <0.05 for this interaction term to indicate a significant treatment effect. These analyses will be further adjusted for baseline characteristics that are prognostic of the outcome, including age, sex, clinical site, and stage of AKI at randomization. Adjustment will be accomplished by adding covariates and interactions of covariates with time.

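### The adjusted MAKE and ordinal models omit AKI stage at randomisation, which the same section treats as prognostic for eGFR and proteinuria, and also omit baseline APACHE-II

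*Combined protocol and SAP*

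**What the plan says.** Section 9.4.3 sets different adjustment lists for its secondary endpoints.

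- **MAKE:** proportional hazards models of time to first event, "without and with adjustment for age, race, clinical site, baseline" serum creatinine, plus Kaplan-Meier curves and a log-rank test.
- **Ordinal outcome (creatinine AUC, dialysis, death):** a cumulative logit model "with terms for treatment, age, gender, clinical site, and baseline serum creatinine".
- **eGFR and proteinuria at 30 and 90 days:** further adjusted for "baseline characteristics that are prognostic of the outcome, including age, sex, clinical site, and stage of AKI at randomization".

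For NAD+ (Section 9.4.2) and creatinine AUC (Section 9.4.3) the plan adds a binary indicator of severe AKI or advanced CKD. MAKE and the ordinal outcome are therefore the only primary or secondary efficacy endpoints with no AKI severity term beyond baseline creatinine. No reason is given.

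Both omitted variables are available at entry. KDIGO staging underlies eligibility (Section 5.1, Table 3). APACHE-II is scheduled at Day 0 and Days 1 to 10 (Section 1.3, Table 1), and the baseline list in Section 8.1 includes "Parameters to assess severity-of-disease using the Acute Physiologic and Chronic Health Evaluation (APACHE) II classification", though only as applicable.

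**The concern.** MAKE and the ordinal outcome are the two endpoints that contain death and dialysis, where severity at entry should matter most. Section 4.2 itself cites a single-centre study that "reported a mortality hazard ratio of 4.7 in Stage 3 AKI patients".

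Baseline creatinine is only a partial substitute. KDIGO stage is a ratio to the patient's own baseline, or a urine-output criterion, so one creatinine value can belong to different stages in different patients. Section 4.2 also warns that admission creatinine may not reflect kidney function before admission. Creatinine does not measure systemic illness.

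Randomisation is stratified by site only (Section 9.4.1), so severity can differ between arms by chance. The results feed decisions. Under the rationale in Section 2.1, a single secondary outcome at p<0.2 without significant harm can support a Phase IIb study, or Phase III if NAD+ also rises, and MAKE is the envisaged Phase III primary endpoint. Section 9.4.3 adds a p≤0.05 trigger for the ordinal outcome, whose only stated model is the adjusted one.

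**Working it through.** **1. The plan's own figures.** Section 9.2 powers NAD+ only, with 40 per arm.

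- Effect size 2.1 gives power above 99.9%, as stated.
- Minimum detectable effect at 80% power: (1.960 + 0.842) × √(2/40) = 0.626, stated as 0.63.
- Section 5.5 expects 15% withdrawal and 5% further attrition: 80 / (1 − 0.20) = 100, matching "A total of 100 participants will be randomized".

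These reproduce. No power, event rate or effect size is stated for MAKE or the ordinal outcome.

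**2. Context for MAKE (Schoenfeld, 1:1, two-sided 5%).** Power = Φ(|ln HR| × √(d/4) − 1.960), with d events.

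- HR 0.5, d = 20: 0.693 × √5 − 1.960 = −0.410, power 34%.
- HR 0.5, d = 40: 0.693 × √10 − 1.960 = 0.232, power 59%.
- 80% power needs 4 × (1.960 + 0.842)² / 0.693², that is 66 events.

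**3. Simulation inputs.**

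From the documents: n = 100; "Participants will be randomly allocated to 1:1 ratio to receive either nicotinamide riboside (NR) or placebo" (Section 6.1.1); "All statistical tests will be two-sided with a significance level of 5" per cent (Section 9.4.1); the planned covariates; and the 4.7, used as one possible Stage 3 effect.

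Assumed:
- Stage 3 effect 4.7 or 2.0.
- Stage 3 share 50% or 75%. The 75% reads the cited threefold excess of Stage 3 (Section 4.2) as 3/(3+1).
- APACHE-II effect 1.5 or 2.0 per SD.
- Baseline creatinine correlated 0.5 with latent AKI severity.
- MAKE: 90-day event rate 20% or 40%; HR 0.4 to 0.6; also n = 80 at HR 0.5. Cox model, Wald test, 1,000 runs per scenario.
- Ordinal: OR 0.3 to 0.5; categories 42/42/8/8%. Proportional odds, likelihood-ratio test, 400 runs per scenario.

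**4. MAKE power (%), n = 100, HR 0.5.**

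| Events | Stage 3 share | Stage 3 HR | APACHE-II HR per SD | Planned | + stage | + stage and APACHE-II | Total gain |
|---|---|---|---|---|---|---|---|
| 20% | 50% | 4.7 | 1.5 | 26.7 | 29.7 | 29.9 | 3.2 |
| 20% | 50% | 4.7 | 2.0 | 22.1 | 24.8 | 26.1 | 4.0 |
| 20% | 50% | 2.0 | 1.5 | 30.1 | 32.1 | 32.5 | 2.4 |
| 20% | 75% | 4.7 | 1.5 | 27.0 | 28.7 | 30.9 | 3.9 |
| 40% | 50% | 4.7 | 1.5 | 42.5 | 51.0 | 53.6 | 11.1 |
| 40% | 50% | 4.7 | 2.0 | 39.5 | 48.6 | 55.5 | 16.0 |
| 40% | 50% | 2.0 | 1.5 | 50.0 | 52.8 | 54.6 | 4.6 |
| 40% | 75% | 4.7 | 1.5 | 51.2 | 55.1 | 57.3 | 6.1 |

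Over all 32 MAKE scenarios the gain from both variables is 1.8 to 16.3 points. It is 1.8 to 6.9 in the 20% event scenarios. It reaches 8 or more in 7 of 32, all with 40% events, Stage 3 HR 4.7 and a 50% Stage 3 share. Stage alone gains 0.6 to 10.1 points.

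**5. Ordinal outcome.** Over 12 scenarios the gain from both variables is 1.5 points (65.0% to 66.5%) to 9.0 points (50.8% to 59.8%), with 8 or more in 1 of 12. Stage alone gains 1.2 to 6.2.

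**6. Further checks.** A separate Cox simulation at HR 0.5 (APACHE-II log HR 0.4 per SD) at the p<0.2 threshold gained about 4, 9 and 10 points at 20%, 30% and 40% events with Stage 3 HR 4.7, and about 2 points at 30% events with Stage 3 HR 2.0. Its null rejection at the 5% level was 5.8% for the planned model and 6.8% with both terms. Another run, with 26 to 27 events, gave 7.1% and 7.7%.

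Monte Carlo error is up to about 1.6 points (MAKE) and 2.5 points (ordinal) per power figure in steps 4 and 5. Models are compared on the same simulated data.

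**The case against.** The best defence is that the plan does not ignore severity. Both models contain baseline creatinine and age, and the MAKE list is the same as the adjusted list for the primary NAD+ analysis. These are secondary endpoints of a pilot that the plan calls exploratory, randomisation protects against bias, and MAKE is also reported unadjusted. APACHE-II may be incomplete, and terms should be few when events are few. All of this stands. It limits the size of the point, but does not explain why stage is used for eGFR and proteinuria and not here.

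Three stronger readings are tempting, and the documents do not support them.

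- A reader might infer that severity is left out altogether. It is not: creatinine and age carry part of it.
- A reader might apply the 4.7 directly to MAKE. It is a mortality figure without a stated comparator. MAKE also counts creatinine doubling and long-term dialysis. Every participant has AKI, and Section 5.2 excludes eGFR below 15 at admission and dialysis before randomisation, so the contrast of Stage 3 with Stages 1-2 may be weaker in this trial.
- A reader might infer a loss of some 8 to 15 points as a property of the plan. Most scenarios gain less, and nothing in the documents fixes the event rate, the treatment effect or the Stage 3 share for this trial.

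**Conclusion.** The omission is real and inconsistent with the rest of Section 9.4.3. Pre-specifying AKI stage, and optionally APACHE-II, would make both adjusted analyses more efficient and would handle chance imbalance. It corrects no bias. Under the stated assumptions the gain is roughly 2 to 16 points of power for MAKE and about 1.5 to 9 for the ordinal outcome, positive in every scenario run but often small. The upper part of the MAKE range needs about 40% events and a strong Stage 3 effect. MAKE stays underpowered either way: 80% power at HR 0.5 needs 66 events, against 20 to 40 in these scenarios. The change is worth making because it is cheap and the secondary results inform whether a later trial goes ahead.

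**What to change.** In Section 9.4.3, before unblinding, add AKI stage at randomisation (Stage 3 versus Stages 1-2) as a pre-specified covariate in the adjusted MAKE model and the ordinal model, in line with the eGFR and proteinuria models. Optionally add baseline APACHE-II, on condition that it is complete enough, with that condition written down in advance. No existing covariate needs to be removed. Keep the unadjusted MAKE model and log-rank test.

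The change needs no extra patients, visits or measurements. The downside is one or two more terms with perhaps 20 to 40 events, and a Wald test error rate slightly above 5% (null rejection about 7 to 8% with both terms in step 6, against about 6 to 7% for the planned model). Left unspecified, any severity adjustment of these two endpoints would be chosen after the fact and carry less weight.

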	4), defined as, in order from least to most severe disease, 1. Serun creatinine $AUC < median$, 2. Serum creatinine $AUC \ge median$, 3. Dialysis, 4. Death;				
	• Time to first occurrence of MAKE (doubling of serum creatinine, the initiation of long-term dialysis, or death from any cause) at 30 d and 90 d post randomization;				
	• Kidney function defined by eGFR and proteinuria at 30d and 90d post randomization.				
	Exploratory				
	• Correlations between whole blood NAD+, AUC serum creatinine, and AKI surrogate markers of AKI such as KIM-1 and NGAL;				
Study Population:	Participants will be >18 years old and admitted to hospital with a laboratory diagnosis of COVID-19 infection and AKI				
Phase:	Phase 2				
Description of	The study is a multicenter study with University of Texas Health San Antonio				
Sites/Facilities	(UTHSA) as the coordinating site. The three recruiting sites are: University				
Enrolling	Hospital affiliated with UTHSA, Icahn School of Medicine at Mount Sinai,				
Participants:	New York, NY and Harborview Medical Center/University of Washington, Seattle, WA				
Description of	The intervention for this clinical trial is Niagen®, a nicotinamide riboside,				
Study	an over the counter nutritional supplement				
Intervention:					
Study Duration	Estimated 2 years				
Participant	The estimated time required for this study will be up to 90 days after				
Duration:	consenting to study protocol. A total of up to 10 visits will occur during the				
	initial 10 days with two follow-up visits -30 days and 90 days from				
	enrollment date.				

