9.4.2 ANALYSIS OF THE PRIMARY EFFICACY ENDPOINT(S)

PRIMARY END POINT: Blood NAD+ level

The null hypothesis to be tested is H₀:R_{NR}=R_{Placebo}, where R_{NR} and R_{Placebo} are the rates of change from baseline to day 10 in the NR and Placebo arms. We expect that the rate of change in NAD+ from baseline to day10 with NR treatment will be increased relative to Placebo. Whole blood NAD+ will be measured daily in each patient during the first 10 days upon randomization. NAD+ level changes from the baseline will be graphically summarized with overlaid line and whisker plots of the mean trajectory for each arm with the whiskers being of length equal to one standard error of the mean. The significance of treatmement group differences with regard to the rate of change of NAD+ will be assessed using the methods of Schluchter et al [86] to address informative censoring, due for example to dialysis and death, with a random subject effect to account for the correlation among repeated measures within an individual. The model will include treatment and day. The day by treatment interaction will be of interest and will be addressed with the coefficient of the day by treatment interaction term to be added to the unadjusted model. Adjusted analyses will be carried out with age, race, clinical site, baseline serum creatinine, treatment and day included in the model. The unadjusted and adjusted models will be summarized with the coefficients, standard errors, 95% confidence intervals and pvalues. A day by treatment interaction term, treatment by day, and treatment by clinical site interactions will be considered and reported and described if found significant (p < 0.10). We will examine potential treatment interactions among subgroups of interest such as age, and sex. Consistent with the power calculation (Section 9.2), these models will be used to provide treatment group contrasts on the mean rate of change (estimated by the coefficient of day in the model, also known as the slope parameter), summarized with the model-based mean rates of changs, mean differences in rates of change and 95% confidence intervals and p-values. Spaghetti plots and plots of the mean NAD+ trajectories by treatment group, and mean rates of change, will be reported.

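### Kidney function is named as an endpoint at Day 30 and Day 90, but the planned test is, on its natural reading, one linear slope with no between-arm contrast at either visit

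*Combined protocol and SAP*

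**What the plan says.** The Synopsis (Section 1.1) gives the endpoint as "Kidney function defined by eGFR and proteinuria at 30d and 90d post randomization", and Table 2 in Section 3 agrees. Section 9.4.3 opens its analysis the same way: "We will quantify kidney dysfunction at 30 days and 90 days post-randomization".

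The hypothesis in that section concerns equal mean rates of change from baseline, with this direction: "We expect the eGFR rate of change to be increased with NR relative to Placebo". The model is described as follows: "We will include time, treatment, and interactions of treatment with time as independent variables in a mixed effects linear model". The measure of effect is a single coefficient: "We will focus on the coefficient for the interaction of treatment with time as the primary measure of treatment effect". The decision rule is also single: "We will consider a p-value <0.05 for this interaction term to indicate a significant treatment effect".

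For dialysis, death and withdrawal, Section 9.4.3 states that "the statistical method will be the same as that specified for NAD"+ applies. Section 9.4.2 describes that method's treatment contrast as one on the mean rate of change, "estimated by the coefficient of day in the model, also known as the slope parameter".

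**The concern.** An endpoint at two visits and a single rate of change are different quantities. They agree only if the treatment difference grows in proportion to time from baseline to Day 90. Nothing in the documents says that it should. Dosing ends at Day 10, and Section 4.3 reports that blood NAD+ peaks at 7 and 14 days with no further rise to Day 56. An early benefit that then holds is therefore at least as plausible as steady growth.

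Two things are at stake. First, the plan specifies no between-arm difference at Day 30 or Day 90, although that is the named endpoint. Second, the p-value has a use: under Section 2.1, any one secondary outcome at p<0.2, without a significant increase in harm, can support a Phase IIb study, or a Phase III study if NAD+ also rises significantly. Section 2.1 also wants the secondary results for planning later trials and foresees a Day 90 primary endpoint there. A slope does not directly supply a Day 90 difference.

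**Working it through.** **The plan's own figure.** No power, SD or effect is given for eGFR or proteinuria. The only figures are for NAD+ (Section 9.2): n = 40 per arm, ρ = 0.5, minimum detectable effect 0.63 SD. The formula (1.960 + 0.842) × √(2/40) gives 0.626, so 0.63 corresponds to 80% power, a level the plan does not state. I borrow n, ρ and 0.63 below for illustration only.

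**Inputs.**
- From the documents: visits at baseline, Day 30 and Day 90; 1:1 allocation; two-sided 5% tests; a model with time, treatment and treatment-by-time.
- Assumed: time linear on a 0/30/90-day grid, exchangeable correlation ρ of 0.4 to 0.8, equal variances, no dropout, ordinary generalised least squares.

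**Slope weights.** Mean time is 40 and the deviations are -40, -10 and 50, so Sxx = 1600 + 100 + 2500 = 4200. For true arm differences (e₀, e₃₀, e₉₀), the slope is (-40e₀ - 10e₃₀ + 50e₉₀)/4200.

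| True difference at 0, 30, 90 | Slope per day | Slope × 30 | Slope × 90 |
|---|---|---|---|
| Sustained: 0, d, d | 40d/4200 = d/105 | 0.29d | 0.86d |
| Day 30 only: 0, d, 0 | -10d/4200 = -d/420 | -0.07d | -0.21d |
| Linear growth: 0, d/3, d | d/90 | 0.33d | 1.00d |

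The model also has a treatment main effect. In the sustained case its value is 2d/3 - 40d/105 = 0.29d. The fitted arm differences are therefore 0.29d at baseline, where randomisation implies none, 0.57d at Day 30 and 1.14d at Day 90. Only the slope is tested.

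Sensitivity to the grid: counting Day 1 as time zero (0/29/89) gives slope-implied gains of 0.28d and 0.85d.

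**Efficiency for the sustained benefit.** Squared signal over variance, leaving out the common factor n/(2σ²):
- Slope: (d/105)² × 4200/(1-ρ) = 0.381d²/(1-ρ)
- Day 90 change score: d²/[2(1-ρ)]
- Day 90 ANCOVA on baseline: d²/(1-ρ²)

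Ratios:
- Slope to change score: 0.381/0.5 = 76% at every ρ, or about 31% more patients (1/0.762).
- Slope to ANCOVA: 0.381(1+ρ) = 53% at ρ = 0.4 and 69% at ρ = 0.8.
- Change score to ANCOVA: (1+ρ)/2 = 70% to 90%. This part of the loss is lack of baseline adjustment, not the straight line.

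**Efficiency if the effect grows linearly.** The slope signal is (d/90)² × 4200/(1-ρ) = 0.519d²/(1-ρ). Against the change score this is 0.519/0.5 = 1.04, about 4% more efficient. Against ANCOVA it is 0.519(1+ρ) = 73% to 93%.

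**Illustration in power.** Take n = 40 per arm, a sustained d = 0.63 SD and ρ = 0.5. Then n·d²/2 = 7.938.
- Slope: z = √(7.938 × 0.381/0.5) = 2.46, power 69%.
- Change score: z = √7.938 = 2.82, power 80%.
- ANCOVA: z = √(7.938/0.75) = 3.25, power 90%.

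**The case against.** The strongest reply is that a slope was chosen for a reason. Section 9.4.3 invokes the NAD+ method to handle dialysis, death and withdrawal as informative censoring. Losses may be material: Section 2.2 reports 9.9% deaths among comparable patients, and Section 5.5 expects 15% withdrawal and a further 5% attrition. Replacing the slope by visit contrasts alone would drop that protection. This stands, and the fix keeps the slope analysis for that purpose. My calculations model no dropout and do not reproduce the planned method.

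A second reply is that the text never says time is continuous. It once speaks of interactions in the plural, and its wording of the hypothesis at Day 30 and Day 90 could mean two comparisons. Nor does it say whether the daily Day 1-10 values enter. This also stands in part. The single coefficient, the single interaction term and the tie to the NAD+ slope make one straight line the natural reading, and the ambiguity itself needs removing.

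Third, a recovery curve shared by both arms does not bias the interaction. Only the shape of the treatment difference matters, and the documents do not give it. Table 2's rationale, that AKI may progress to CKD, is compatible with a difference that grows. That is correct: an early, sustained benefit is a scenario here and not a documented fact.

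Finally, this is one secondary endpoint in a pilot that Section 9.4.1 calls exploratory. That limits the weight of the point but does not remove the mismatch.

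**Conclusion.** The endpoint and its test do not match. On the natural reading, the plan tests one linear slope and specifies no between-arm contrast at Day 30 or Day 90. For a sustained benefit, the slope-implied gain falls 71% short at Day 30 and 14% short at Day 90. For a benefit at Day 30 only, the slope has the wrong sign. The weights follow from the visit days once time is taken as linear; the efficiency and power figures also depend on the assumed correlation, equal variances and absence of dropout.

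Three stronger readings are not supported:
- A reader might infer that the model's fitted Day 30 difference is only 29% of the truth. That figure is the slope-implied gain from baseline; the fitted arm difference is 0.57d.
- A reader might infer that the plan yields no information at Day 30 or Day 90. Section 9.4.1 provides descriptive summaries by treatment. What is missing is a specified comparison.
- A reader might attribute the whole loss against ANCOVA to the straight line. Part of it is the missing baseline adjustment.

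The stated sample size rests on NAD+ and is unaffected. This should be changed, but it does not threaten the trial's primary conclusions.

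**What to change.** In the kidney impairment part of Section 9.4.3:
- Treat visit as categorical (baseline, Day 30, Day 90) with a common baseline mean in the two arms.
- Report baseline-adjusted treatment differences with 95% CIs at Day 30 and Day 90, for eGFR and for log proteinuria, with Day 90 named as the main contrast.
- Keep the treatment-by-time slope, fitted under the plan's informative-censoring method, as a supportive and sensitivity analysis, so that the stated handling of death, dialysis and withdrawal is retained.
- State the coding of time in the slope model and whether the Day 1-10 values enter it.

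The cost is SAP wording and a little more analysis. The real downside is that the visit contrasts rest on missing at random unless they are read together with that sensitivity analysis. On the assumptions above there is no efficiency loss at Day 90: even under linear growth the planned slope is 73-93% as efficient as the baseline-adjusted Day 90 ANCOVA.
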